12.3. Measurement of Effect

Progressive standard prostate cancer is often manifest by rising PSA levels, new lesions on bone scan, new disease-related symptoms and increasing size of a measurable soft tissue mass. Response is commonly assessed either biochemically (PSA change) or by change in size of a measurable lesion/s. Given that patients with NEPC do not often secrete PSA and all patients on study will have measurable disease, the primary outcome will be determined by radiologic response and progression. PSA response rate is a secondary endpoint.

12.3.1 Change in lesion size

Complete response (CR) is defined as complete disappearance of all measurable and evaluable lesions by physical examination or imaging studies and normalization of PSA with no appearance of new lesions for > 1 month. Partial response (PR) is defined as a 30%

or greater reduction in the sum longest unidimensional diameter of all measurable lesions. There may be no new lesions. Stable Disease (SD) is characterized by patients who do not meet the criteria of PR and who are without signs of progressive disease for at least 1 month. Disease Progression (DP) is defined as a greater than 20% increase in the sum longest unidimensional diameters of the indicator lesions or the appearance of new lesions. Bone scan progression (evaluable disease only) is defined by PCWG2 criteria. Per consensus guidelines in CRPC, to be considered measurable, lymph nodes need to be at least 2 cm in greatest dimension and 1.5 cm in short axis. [32 and RECIST 1.1]

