5.2.10 Radiographic evaluation – See Section 7.0

To be performed after cycle 3, and following every 3rd subsequent cycle, or as clinically indicated.

Consideration should be made for confirmatory scans after 4 weeks should criteria for PR or CR by RECIST be met at any imaging time point.

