7.0 Radiographic evaluation

The following radiographic evaluations must be performed according to the schedule outlined below:

- Bone scan, CT/MRI abdomen/pelvis, and CT of chest at baseline
- Bone scan, CT/MRI of abdomen/pelvis, and CT of chest will be repeated after every 3rd cycle until the subject is off-study
- In addition, scans will be performed for subjects with clinical signs or symptoms of progression at the investigators discretion
- Every effort should be made to use the same imaging technique for follow up evaluation as was utilized at baseline
- Should RECIST criteria for PR or CR be met at any imaging time point, investigators are urged to consider a repeat scan at least 4 weeks following the scan demonstrating response. In this instance, or if imaging is performed for clinical purposes earlier than scheduled per protocol, it is permissible to “reset” future imaging time points to every 3rd cycle following the last scan.

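### A radiologic complete response is made to depend on PSA, and the protocol does not fix whether a response must be confirmed

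*Protocol*

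**What the plan says.** The protocol summary lists radiologic response rate as a secondary objective. Its Study Design and Duration of Intervention paragraphs say response is evaluated by CT/MRI and bone scan every 3 cycles and determined by RECIST v1.1. Section 3.0 says the same and adds PCWG2 modifications. None of these places mentions PSA as part of response.

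Section 12.3 says the outcome is radiologic because these patients often do not secrete PSA and because all of them will have measurable disease. It adds that "PSA response rate is a secondary endpoint".

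Section 12.3.1 then gives the working definitions:
- CR is "complete disappearance of all measurable and evaluable lesions by physical examination or imaging studies and normalization of PSA". A time element follows: "normalization of PSA with no appearance of new lesions for > 1 month".
- PR is a 30% "or greater reduction in the sum longest unidimensional diameter of all measurable lesions. There may be no new lesions". It carries no duration, confirmation or PSA condition.

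On confirming scans, section 5.2.10 says: "Consideration should be made for confirmatory scans after 4 weeks should criteria for PR or CR by RECIST be met at any imaging time point". Section 7.0 says that "investigators are urged to consider a repeat scan at least 4 weeks following the scan demonstrating response", and that afterwards "it is permissible to “reset” future imaging time points to every 3rd cycle following the last scan". Scheduled imaging "will be repeated after every 3rd cycle until the subject is off-study".

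Section 12 analyses the radiologic response rate as a binomial proportion with a 95% confidence interval. In section 10.0, the DSMB text says that if at least 4 subjects have a protocol-defined response before the 19th is enrolled, enrollment continues without a halt.

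**The concern.** The endpoint is called radiologic, the assessments listed for it are imaging, and the stated reason for relying on imaging is that PSA is often uninformative here. A CR definition that a PSA value can veto goes against all three. It also brings a separately reported secondary endpoint into this one. No level is given for a normal PSA, and the clause does nothing in a patient whose PSA is normal at baseline.

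Confirmation is uneven as well. Section 12.3.2 requires serum-marker declines to be confirmed at least 2 weeks later, while a PR in section 12.3.1 needs no second look and the confirming scan is discretionary. In a single-arm trial the response rate has no control arm in which the same measurement error would also appear, so a reader must know which kind of response was counted.

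Three uses are at stake: the reported CR and response rates, the exploratory analyses that relate response to Aurora-A and N-myc status, and the DSMB rule, which acts during enrollment.

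**Working it through.** The protocol states no assumed or target response rate, so there is no figure of its own to reproduce. The check is mainly logical.

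**1. Effect of the PSA clause, taking section 12.3.1 as written**

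| Patient | PSA normalizes | PSA does not |
|---|---|---|
| Measurable disease, all lesions gone, no new lesions | CR | Fall in sum is 100%, which is at least 30%: PR |
| No measurable disease, all evaluable lesions gone, no new lesions | CR | PR unavailable (no sum of diameters): not a responder |

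In the first row CR+PR is the same either way and only the split moves. In the second row PSA alone decides response. Section 12.3 says every patient will have measurable disease, but section 4.3 as printed does not require it, and section 12.3.1 itself provides for evaluable-only disease in bone.

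**2. Effect of the optional rescan**

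- Scheduled interval: 3 cycles × 21 days = 63 days, about 9 weeks.
- Optional rescan: at least 4 weeks = 28 days after the scan showing response.
- PR as written needs one qualifying scan, so a rescan does not decide whether it counts.
- CR needs more than 1 month without new lesions, so some later scan must show this. A patient rescanned at 5 weeks can meet it. The same patient, not rescanned and off study before week 9, cannot, and is counted as PR.
- A confirmed rate behaves in the same way: an early rescan can confirm a response that would otherwise go unconfirmed if the patient leaves before the next scheduled scan.

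**3. Size, by illustration only**

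Assumptions, none from the protocol: 20% of patients have an unconfirmed response, and a share c of these is confirmed. Responders among 60 patients = 60 × 0.20 × c. The trigger probability is the chance of at least 4 responses among the first 18 subjects, P = 1 − Σ(k=0..3) C(18,k) p^k (1−p)^(18−k), with p = 0.20 × c.

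| c | p | Responders of 60 | Exact 95% CI | P(at least 4 of 18) |
|---|---|---|---|---|
| 0.50 | 0.10 | 6 | 3.8% to 20.5% | 0.10 |
| 0.75 | 0.15 | 9 | 7.1% to 26.6% | 0.28 |
| 1.00 | 0.20 | 12 | 10.8% to 32.3% | 0.50 |

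With an unconfirmed rate of 10% to 30% and c from 0.50 to 1.00, p runs from 0.05 to 0.30 and P from 0.01 to 0.84. These figures treat all 18 subjects as already assessed, which flatters every row.

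**4. Primary rule**

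For n = 48 and success at 12 or more, the exact one-sided alpha at 15% is 0.048 and the power at 30% is 0.819, as the protocol claims. The endpoint is freedom from radiographic progression, so neither the CR nor the PR definition enters.

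**The case against.** The strongest reply is that this is a secondary endpoint, that the analysed quantity is the overall rate, and that in measurable disease the PSA clause cannot change that rate. This stands. Whether to report confirmed or unconfirmed response is also commonly settled in a statistical analysis plan, which is not shown here, so that silence alone would not be a finding. But the CR wording is fixed in this protocol, and the DSMB trigger relies on a definition in this protocol.

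A second reply is that the protocol announces PCWG2 modifications, and that the named criteria might themselves allow a marker condition. Neither source is reproduced in the document, so this cannot be settled here. The conflict rests on the protocol's own text: the endpoint's name, the imaging assessments listed for it, and the rationale in section 12.3.

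A reader might go further and infer three things that the document does not support:
- That the overall response rate depends on who chose to rescan. An unconfirmed PR counts under section 12.3.1 whether or not anyone rescans.
- That CR must persist for more than a month. The month is attached to the absence of new lesions, not clearly to the continued absence of the old ones.
- That false-positive local reads inflate the rate. The sections on imaging do not say who reads the scans, and the protocol gives no measurement error from which to calculate such an effect.

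**Conclusion.** The point holds in a limited form and should be corrected. The PSA condition for CR is inconsistent with how the protocol describes and justifies the endpoint. In measurable disease it moves patients from CR to PR without changing CR+PR. In any patient without measurable disease it could decide response; how many there would be is unknown, and none if section 12.3 is right about the population.

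Because confirmation is optional, the CR rate and any confirmed rate could vary with investigator choice, while the unconfirmed CR+PR rate in measurable disease does not. The DSMB trigger has no single meaning: it does not say whether confirmation is needed, or whether the radiologic response is meant at all, since section 12.3.2 also defines serum-marker responses. The probabilities shown for it rest entirely on assumed response and confirmation rates. The primary decision rule is untouched.

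**What to change.** - In section 12.3.1, delete the PSA condition from CR so that CR and PR rest on imaging alone. PSA response continues to be reported under section 12.3.2.
- In section 12, report two rates side by side: unconfirmed response, and confirmed response, meaning that the criteria are still met on a scan at least 4 weeks later. State in sections 5.2.10 and 7.0 that the next scheduled scan, at about 9 weeks, suffices. No extra imaging is then required.
- In the DSMB text of section 10.0, state that radiologic response is meant and which of the two rates counts.

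The cost is a few lines of wording and one extra reported rate. The confirmed rate will be the lower one, and a responder who leaves the study before the next scan counts as unconfirmed, which is why both should be shown. If the trigger uses confirmed response from scheduled scans alone, a response needs about 9 + 9 = 18 weeks from first treatment instead of about 9, so fewer of the first 18 subjects could qualify in time. That choice should be made knowingly.

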12.3.2 Serum marker response (PSA, chromogranin, neuron specific enolase)

Serum PSA, chromogranin, and neuron specific enolase (NSE) responses are determined by comparing the nadir level after therapy to the baseline, pre-treatment level determined just prior to initiating therapy. Declines of $\geq 30\%$ and 50% , confirmed by a value ≥ 2 weeks later, will be reported. Serum marker progression will be defined as a rise of $> 25\%$ above either the pretreatment level or the nadir level (whichever is lowest). PSA must increase by > 2 ng/ml to be considered progression. Confirmation requires a second consecutive rising PSA, chromogranin, or NSE at least 2 weeks apart. Marker stabilization is referred to as any set of values that do not meet the criteria for response or PSA progression.

12.3.3 CTC count response (CellSearch). Baseline CTC counts of < 5 when measured by CellSearch methodology have been associated with better prognosis (overall survival).[34, 35] In addition, changes in CTC counts after initial therapy have been demonstrated to be predictive.[36] We will explore the prognostic and predictive significance of 4 groups as has been described:

Baseline < 5 , follow up < 5
Baseline ≥ 5 , follow up < 5
Baseline < 5 , follow up ≥ 5
Baseline ≥ 5 , follow up ≥ 5

In addition, we will report individual subject's CTC count change from baseline.

13.0 Data Collection The data collection plan for this study is to utilize a study-specific (WCMC CTSC-supported) REDCap database to capture all treatment, toxicity, and efficacy data for all enrolled patients.

13.1 Confidentiality In order to protect confidentiality of the data, patient full names will be removed and data coded with patient initials and study subject numbers. All primary data will be kept in locked file cabinets or password-protected computers and available only to the investigators and appropriate regulatory personnel (e.g., IRB, FDA, etc.).

14.0 ADMINISTRATIVE REQUIREMENTS

Good Clinical Practice

The study will be conducted in accordance with the International Conference on Harmonisation (ICH) for Good Clinical Practice (GCP) and the appropriate regulatory requirement(s). The investigator will be thoroughly familiar with the appropriate use of the drug as described in the protocol and Investigator's Brochure. Essential clinical documents will be maintained to demonstrate the validity of the study and the integrity of the data collected. Master files should be established at the beginning of the study, maintained for the duration of the study and retained according to the appropriate regulations.

Ethical Considerations

The study will be conducted in accordance with ethical principles founded in the Declaration of Helsinki (see Section 0). The IRB/IEC will review all appropriate study documentation in order to safeguard the rights, safety and well-being of the patients. The study will only be conducted at sites where IRB/IEC approval has been obtained. The protocol, Investigator's Brochure, informed consent, advertisements (if applicable), written information given to the patients (including diary cards), safety updates, annual progress reports, and any revisions to these documents will be provided to the IRB/IEC by the investigator. Millennium requests that informed consent documents be reviewed by Millennium or designee prior to IRB/IEC submission.

Patient Information and Informed Consent

After the study has been fully explained, written informed consent will be obtained from either the patient or his/her guardian or legal representative prior to study participation. The method of obtaining and documenting the informed consent and the contents of the consent will comply with ICH-GCP and all applicable regulatory requirement(s).

Patient Confidentiality

In order to maintain patient privacy, all data capture records, drug accountability records, study reports and communications will identify the patient by initials and the assigned patient number. The investigator will grant monitor(s) and auditor(s) from WCMC or its designees and regulatory authority(ies) access to the patient's original medical records for verification of data gathered on the data capture records and to audit the data collection process. The patient's confidentiality will be maintained and will not be made publicly available to the extent permitted by the applicable laws and regulations.

Protocol Compliance

The investigator will conduct the study in compliance with the protocol given approval/favorable opinion by the IRB/IEC and the appropriate regulatory authority(ies). Significant changes to the protocol will require approval from Millennium and written IRB/IEC approval/favorable opinion prior to implementation, except when the modification is needed to eliminate an immediate hazard(s) to patients. The IRB/IEC may provide, if applicable regulatory authority(ies) permit, expedited review and approval/favorable opinion for minor change(s) in ongoing studies that have the approval /favorable opinion of the IRB/IEC. The investigator will submit all protocol modifications to Millennium and the regulatory authority(ies) in accordance with the governing regulations.

Any departures from the protocol must be fully documented in the source documents.

On-site Audits

Regulatory authorities, the IEC/IRB, WCMC personnel or their delegates and/or Millennium's clinical quality assurance group may request access to all source documents, data capture records, and other study documentation for on-site audit or inspection. Direct access to these documents must be guaranteed by the investigator, who must provide support at all times for these activities.

Drug Accountability

Accountability for the drug at all study sites is the responsibility of the principal investigator. The investigator will ensure that the drug is used only in accordance with this protocol. Drug accountability records indicating the drug's delivery date to the site (if applicable), inventory at the site (if applicable), use by each patient, and return to Millennium or disposal of the drug (if applicable and if approved by Millennium) will be maintained by the clinical site. Accountability records will include dates, quantities, lot numbers, expiration dates (if applicable), and patient numbers.

All material containing MLN8237 will be returned to Millennium Pharmaceuticals, Inc.

Premature Closure of the Study

This study may be prematurely terminated, if in the opinion of the investigator, WCMC, or Millennium, there is sufficient reasonable cause. Written notification documenting the reason for study termination will be provided to the investigator, WCMC, or Millennium by the terminating party.

Circumstances that may warrant termination include, but are not limited to:

- Determination of unexpected, significant, or unacceptable risk to patients
- Failure to enter patients at an acceptable rate

- Insufficient adherence to protocol requirements
- Insufficient complete and/or evaluable data
- Plans to modify, suspend or discontinue the development of the drug

Should the study be closed prematurely, all study materials must be returned to Millennium.

Record Retention

The investigator will maintain all study records according to ICH-GCP and applicable regulatory requirement(s).

3. The Declaration of Geneva of the World Medical Association binds the physician with the words, "The health of my patient will be my first consideration," and the International Code of Medical Ethics declares that, "A physician shall act only in the patient's interest when providing medical care which might have the effect of weakening the physical and mental condition of the patient."
4. Medical progress is based on research which ultimately must rest in part on experimentation involving human subjects.
5. In medical research on human subjects, considerations related to the well-being of the human subject should take precedence over the interests of science and society.
6. The primary purpose of medical research involving human subjects is to improve prophylactic, diagnostic and therapeutic procedures and the understanding of the aetiology and pathogenesis of disease. Even the best proven prophylactic, diagnostic, and therapeutic methods must continuously be challenged through research for their effectiveness, efficiency, accessibility and quality.
7. In current medical practice and in medical research, most prophylactic, diagnostic and therapeutic procedures involve risks and burdens.
8. Medical research is subject to ethical standards that promote respect for all human beings and protect their health and rights. Some research populations are vulnerable and need special protection. The particular needs of the economically and medically disadvantaged must be recognized. Special attention is also required for those who cannot give or refuse consent for themselves, for those who may be subject to giving consent under duress, for those who will not benefit personally from the research and for those for whom the research is combined with care.
9. Research Investigators should be aware of the ethical, legal and regulatory requirements for research on human subjects in their own countries as well as applicable international requirements. No national ethical, legal or regulatory requirement should be allowed to reduce or eliminate any of the protections for human subjects set forth in this Declaration.

B. BASIC PRINCIPLES FOR ALL MEDICAL RESEARCH

1. It is the duty of the physician in medical research to protect the life, health, privacy, and dignity of the human subject.
2. Medical research involving human subjects must conform to generally accepted scientific principles, be based on a thorough knowledge of the scientific literature, other relevant sources of information, and on adequate laboratory and, where appropriate, animal experimentation.
3. Appropriate caution must be exercised in the conduct of research which may affect the environment, and the welfare of animals used for research must be respected.
4. The design and performance of each experimental procedure involving human subjects should be clearly formulated in an experimental protocol. This protocol should be submitted for consideration, comment, guidance, and where appropriate, approval to a specially appointed ethical review committee, which must be independent of the investigator, the sponsor or any other kind of undue influence. This independent committee should be in conformity with the laws and regulations of the country in which the research experiment is performed. The committee has the right to monitor ongoing trials. The researcher has the obligation to provide monitoring information to the committee, especially any serious adverse events. The researcher should also submit to the committee, for review, information regarding funding, sponsors, institutional affiliations, other potential conflicts of interest and incentives for subjects.
5. The research protocol should always contain a statement of the ethical considerations involved and should indicate that there is compliance with the principles enunciated in this Declaration.
6. Medical research involving human subjects should be conducted only by scientifically qualified persons and under the supervision of a clinically competent medical person. The responsibility for the human subject must always rest with a medically qualified person and never rest on the subject of the research, even though the subject has given consent.
7. Every medical research project involving human subjects should be preceded by careful assessment of predictable risks and burdens in comparison with foreseeable benefits to the subject or to others. This does not preclude the participation of healthy volunteers in medical research. The design of all studies should be publicly available.
8. Physicians should abstain from engaging in research projects involving human subjects unless they are confident that the risks involved have been adequately assessed and can be satisfactorily managed. Physicians should cease any investigation if the risks are found to outweigh the potential benefits or if there is conclusive proof of positive and beneficial results.
9. Medical research involving human subjects should only be conducted if the importance of the objective outweighs the inherent risks and burdens to the subject. This is especially important when the human subjects are healthy volunteers.
10. Medical research is only justified if there is a reasonable likelihood that the populations in which the research is carried out stand to benefit from the results of the research.
11. The subjects must be volunteers and informed participants in the research project.
12. The right of research subjects to safeguard their integrity must always be respected. Every precaution should be taken to respect the privacy of the subject, the confidentiality of the patient's information and to minimize the impact of the study on the subject's physical and mental integrity and on the personality of the subject.

13. In any research on human beings, each potential subject must be adequately informed of the aims, methods, sources of funding, any possible conflicts of interest, institutional affiliations of the researcher, the anticipated benefits and potential risks of the study and the discomfort it may entail. The subject should be informed of the right to abstain from participation in the study or to withdraw consent to participate at any time without reprisal. After ensuring that the subject has understood the information, the physician should then obtain the subject's freely-given informed consent, preferably in writing. If the consent cannot be obtained in writing, the non-written consent must be formally documented and witnessed.
14. When obtaining informed consent for the research project the physician should be particularly cautious if the subject is in a dependent relationship with the physician or may consent under duress. In that case the informed consent should be obtained by a well-informed physician who is not engaged in the investigation and who is completely independent of this relationship.
15. For a research subject who is legally incompetent, physically or mentally incapable of giving consent or is a legally incompetent minor, the investigator must obtain informed consent from the legally authorized representative in accordance with applicable law. These groups should not be included in research unless the research is necessary to promote the health of the population represented and this research cannot instead be performed on legally competent persons.
16. When a subject deemed legally incompetent, such as a minor child, is able to give assent to decisions about participation in research, the investigator must obtain that assent in addition to the consent of the legally authorized representative.
17. Research on individuals from whom it is not possible to obtain consent, including proxy or advance consent, should be done only if the physical/mental condition that prevents obtaining informed consent is a necessary characteristic of the research population. The specific reasons for involving research subjects with a condition that renders them unable to give informed consent should be stated in the experimental protocol for consideration and approval of the review committee. The protocol should state that consent to remain in the research should be obtained as soon as possible from the individual or a legally authorized surrogate.
18. Both authors and publishers have ethical obligations. In publication of the results of research, the investigators are obliged to preserve the accuracy of the results. Negative as well as positive results should be published or otherwise publicly available. Sources of funding, institutional affiliations and any possible conflicts of interest should be declared in the publication. Reports of experimentation not in accordance with the principles laid down in this Declaration should not be accepted for publication.

C. ADDITIONAL PRINCIPLES FOR MEDICAL RESEARCH COMBINED WITH MEDICAL CARE

1. The physician may combine medical research with medical care, only to the extent that the research is justified by its potential prophylactic, diagnostic or therapeutic value. When medical research is combined with medical care, additional standards apply to protect the patients who are research subjects.
2. The benefits, risks, burdens and effectiveness of a new method should be tested against those of the best current prophylactic, diagnostic, and therapeutic methods. This does not exclude the use of placebo, or no treatment, in studies where no proven prophylactic, diagnostic or therapeutic method exists.

3. At the conclusion of the study, every patient entered into the study should be assured of access to the best proven prophylactic, diagnostic and therapeutic methods identified by the study.
4. The physician should fully inform the patient which aspects of the care are related to the research. The refusal of a patient to participate in a study must never interfere with the patient-physician relationship.
5. In the treatment of a patient, where proven prophylactic, diagnostic and therapeutic methods do not exist or have been ineffective, the physician, with informed consent from the patient, must be free to use unproven or new prophylactic, diagnostic and therapeutic measures, if in the physician's judgement it offers hope of saving life, re-establishing health or alleviating suffering. Where possible, these measures should be made the object of research, designed to evaluate their safety and efficacy. In all cases, new information should be recorded and, where appropriate, published. The other relevant guidelines of this Declaration should be followed.

APPENDIX 2

Common Terminology Criteria for Adverse Events Version 4.0x

Available at:

<http://ctep.cancer.gov/reporting/ctc.html>

APPENDIX 3

Study Steering Committee

The initial protocol has been designed by WCMC investigators in collaboration from external investigators and input from Millennium Pharmaceuticals.

In the event that protocol discrepancies arise or future amendments are deemed necessary, a discussion with investigators may occur. Ultimate decisions affecting the protocol, including amendments, future analyses, and presentation/publication will be determined by the Steering Committee, comprised of:

- WCMC Core Investigators ([name], [name], [name])
- PCCTC Sponsor
- Additional external Investigator
